Ascertainment of AKI is a potential issue for measurement bias. By focusing on patients with pre-existing CKD, we will limit the number of patients currently without measurement of serum creatinine up to 48- hours. Based on our extensive experience with the CART data and supplementary serum creatinine data from multiple sources within the VA, less than 5% of patients with pre-existing CKD do not have a post-procedure serum creatinine measured within 48-hours. Current VA standard of care is to have post-procedure serum creatinine measured for all CKD patients. We will strongly encourage sites to implement a routine clinical practice that is in compliance with the current guidelines as part of our educational quality improvement framework.

While setting up the study, we will be able to collect data from sites for a period of approximately 6-months before any interventions are unleashed. One strategy is to use these data to establish baseline covariates for each site, helping to account for unexplained variation between sites. However, with the ICC estimated to only be 0.0009, there is likely to be little utility in this. Another use is to allow the 4 intervention strategies to be compared to a pure control or baseline in which no intervention is used by pooling these data with the data.

PROTOCOL

(Version #: 6, version date: 9-21-20)

C.15. Specific Aim 2: Evaluate the sustained efficacy of the Virtual Learning Collaborative and/or Automated Surveillance Reporting to reduce the incidence of AKI following the intervention period.

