Prior studies using the Veterans Health Administration coronary angiography cohort have developed robust, externally validated prediction models for AKI; however, it is still unclear if certain less well-studied laboratory markers in this context are risk factors for AKI. Hypomagnesemia, for example, is associated with a higher risk of AKI in patients receiving cisplatin, as well as in non-cancer patients. In a cohort of ~20,000 cardiac surgery patients, we found that hypomagnesemia (defined as a serum magnesium level <1.5 mg/dl) is associated with a 1.8-fold higher odds of the composite outcome of severe AKI, need for renal replacement therapy (RRT), or death, even after multivariable adjustment. We also found that lower pre-procedure hemoglobin and higher hemoglobin A1c are each independently associated with a higher risk of AKI after cardiac surgery.

Study Design: In this specific aim, we will examine whether lower serum magnesium, lower hemoglobin, higher hemoglobin A1c, and other laboratory predictors are associated with a higher risk of AKI in patients undergoing coronary angiography. We will also examine whether laboratory predictors are associated with an increased risk of

PROTOCOL

(Version #: 6, version date: 9-21-20)

death at 30 days. The exposures will vary based on the individual analyses; however, the inclusion and exclusion criteria will be the same:

Data Collection: The cohort of interest will be all patients undergoing cardiac catheterization in the VA, per the parent data collection above.

Inclusion criteria: VA adult patients who underwent coronary angiography during the last 10 years (2008 to 2018)

Exclusion criteria:

- End-stage renal disease (ESRD) on dialysis
- Missing baseline SCr
- No post-procedure SCr available within 7 days
- Missing a pre-procedure value of the laboratory predictor of interest (e.g., magnesium, HbA1c, hemoglobin)
- AKI at the time of coronary angio, defined as a ≥ 2 -fold increase in SCr from baseline value to most proximal value prior to coronary angio or any RRT within 7 days prior

Primary Endpoints: Major Adverse Kidney Event within 7 days (MAKE7_1 or MAKE7_2), defined as ≥ 1.5 -fold or ≥ 2 -fold increase in SCr within 7 days, need for RRT within 7 days, or death within 7 days. We are defining AKI as a doubling of serum creatinine (SCr) or need for RRT.

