Statistical Analysis: We will conduct a multivariate analysis for the outcome of the primary endpoints as noted above, adjusted for the covariates already described in the prior aims, namely patient demographics, laboratory tests, medication administrations, and numerous clinical conditions defined as combinations of administrative codes.

D. Performance Sites:

- The Dartmouth Institute for Health Policy & Clinical Practice, Epidemiology, Biomedical Data Science at the Geisel School of Medicine at Dartmouth College—*Coordinating site* (Affiliate of White River Junction VA)
- Vanderbilt University, Department of Biomedical Informatics, Vanderbilt University Medical Center (Affiliate of TVHS VA)
- Tennessee Valley Healthcare Systems, Department of Veteran Affairs
- University of Vermont, University of Vermont Medical Center

E. Study Population:

E.1. Patients

E.1.a. Inclusion Criteria for VA Patients

The following conditions must be met for study eligibility:

- 1) Adults are defined as those patients aged 18 or greater
- 2) All patients presenting for diagnostic coronary angiography or percutaneous coronary intervention (PCI or angioplasty) to one of the enrolled VA hospitals will be enrolled in the trial. CKD is of primary interest and it will be determined by a

PROTOCOL

(Version #: 6, version date: 9-21-20)

pre-existing CKD diagnosis in the VA medical record, or by two or more estimated glomerular filtration rates <60 (ml/min/1.73 m 2) at least 90-days apart prior to presentation.

E.1.b. Exclusion Criteria for VA Patients

Patients meeting any of the following criteria will not be eligible to participate in the study:

- 1) Patients with a history of dialysis including hemodialysis, or peritoneal dialysis.

E.2. Implementation Site Staff

All staff members participating in team-based interventions will be interviewed at baseline, 12, and 18 months following the Virtual Learning Collaborative and Technical Assistance interventions. We estimate to interview 5 to 10 staff members at each of the 16 sites participating in the study. The staff members will include the cardiac catheterization laboratory director, nurse managers, cardiologists, nephrologists, and technicians.

F. Research Specific Risks:

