The risks involved in the participation in this study are very minimal and are outweighed by the potential benefits. There is no physical testing or additional laboratory testing involved beyond routine care. Only standard clinical practice will be implemented with improvements to that practice. No research interventions or tests will be conducted, only team-based interventions and automated reports to operators for the continuous improvement of routine care. Patients without a post-procedural laboratory completed for serum creatinine at the time of discharge will be sent home with laboratory orders (slips) for completion at 48 hours. Post-procedure laboratory measurement of serum creatinine is routine safe and effective care for patients with pre-existing CKD as the development of AKI is associated with a higher risk of short- and long-term mortality and renal failure.

F.1 Recruitment and Informed Consent

F.1.1. Recruitment Strategy

All VA Medical Centers have been recruited for the study and agreed to randomization. All patients meeting eligibility criteria will be enrolled in the study. Therefore, patient recruitment will not be performed at each site. Data on all cardiac catheterization patients will be pulled to the data core. Patient eligibility will be determined both at each VA site and by the data core. Each site will ensure data fields are populated and follow-up serum creatinine is measured. The data core will determine eligibility and populate analytic datasets for both bi-weekly automated surveillance reports and for the final statistical analysis of the study.

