This study has the potential to substantially add to the evidence base and scientific knowledge on the sustainable adoption of AKI preventive strategies delivered through inexpensive team-based coaching programs and simple automated reports to catheterization laboratory operators. The successful implementation of the AKI preventive strategies will reduce the incidence of AKI and likely prevent progression of CKD, ESRD, and mortality as demonstrated in our previous research. Given the number of preventive strategies for AKI, it is essential to learn how to engage teams and hospitals to implement and sustain those preventive strategies in order to prevent AKI and other long-term consequences of AKI. While our study will focus on the implementation of AKI preventive strategies, the results of our study could be applied to the implementation of other patient-safety interventions in cardiac catheterization laboratories. By collecting implementation data, we will better understand how to successfully disseminate AKI preventive strategies to hospitals across the United States and the world.

Cost and Compensation: There will not be any costs or compensation to subjects.

Medical Record Review:

Data for this study will be collected prospectively through the VA electronic medical record. Routine data feeds will populate the database at the data core under the supervision of [name]. All data elements from the NCDR cardiac catheterization national database, which is sent to CART in Denver, CO, will be sent to the data core. All patient laboratory results (in- and out-patient) will be sent to the data core. Automated surveillance reports will only include de-identified data and in aggregate form. Once the trial is complete, a de-identified dataset will be created for statistical analysis. The analysis will be conducted within the VA and not transported outside the VA to ensure data security.

References

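### Aim 3's 7-day creatinine exclusion removes untested early deaths that meet its own primary endpoint and, on the most natural reading, also restricts the 30-day death cohort

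*Protocol*

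**What the plan says.** All of the relevant text is in Protocol C.23 (Specific Aim 3), apart from a few remarks on testing elsewhere.

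- **Exclusion criteria:** patients with "No post-procedure SCr available within 7 days" leave the cohort.
- **Primary Endpoints:** MAKE7 is a creatinine rise (1.5-fold or 2-fold, giving two versions), "need for RRT within 7 days, or death within 7 days".
- **Study Design:** after naming the predictors and AKI, the text adds "death at 30 days. The exposures will vary based on the individual analyses; however, the inclusion and exclusion criteria will be the same". One list of criteria follows, with no exception by outcome.
- **Data Collection:** "The cohort of interest will be all patients undergoing cardiac catheterization in the VA". The inclusion criterion limits this to adults with angiography from 2008 to 2018. It is not restricted to chronic kidney disease (CKD).
- **Statistical Analysis:** "We will conduct a multivariate analysis for the outcome of the primary endpoints as noted above", with covariate adjustment. There is no rule for missing creatinine, no exception for death or RRT, and no sensitivity analysis.

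The SAP describes only the trial's AKI models and does not mention Aim 3.

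On testing, Protocol C.14 says that "less than 5% of patients with pre-existing CKD do not have a post-procedure serum creatinine measured within 48-hours". Section F says "Patients without a post-procedural laboratory completed for serum creatinine at the time of discharge will be sent home with laboratory orders". The Medical Record Review section says "All patient laboratory results (in- and out-patient) will be sent to the data core".

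**The concern.** Entry to the cohort depends on something that happens after the procedure and that the outcome itself can prevent. Death soon after the procedure can occur before any blood is drawn. The endpoint needs no creatinine to count that death, yet the exclusion deletes it. Covariate adjustment cannot restore a deleted event.

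For 30-day death the requirement has no measurement purpose, because vital status does not depend on a creatinine value. If the exclusion applies there, that cohort is selected on a test the outcome does not need.

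At stake are the event rates and the predictor associations for MAKE7 and, if the list applies, for 30-day death. The exclusion is reasonable for the creatinine-based AKI outcome.

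**Working it through.** The documents give no event rate, untested share, sample size or power figure for Aim 3, so there is no planned figure to reproduce. The first step is logical; the rest is illustration with assumed inputs.

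**1. Exclusion against endpoint.** Both use a 7-day window. Two of the three MAKE7 components (RRT, death) need no creatinine. A patient with any creatinine between the procedure and the event stays in, so only untested events are lost.

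**2. MAKE7, unadjusted.** Assumed: non-fatal creatinine events e = 3% in both groups; 7-day death d = 2% exposed, 1% unexposed; q = share of deaths untested; m = share of 7-day survivors untested.

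True risks are 5% and 4%, so the true OR = (0.05/0.95)/(0.04/0.96) = 1.263.

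Risk under the current rule = [e(1−m) + d(1−q)] / [(1−d)(1−m) + d(1−q)].

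Example with q = 0.25, m = 0.05: exposed (0.0285 + 0.0150)/(0.9310 + 0.0150) = 0.0435/0.9460 = 4.60%; unexposed (0.0285 + 0.0075)/(0.9405 + 0.0075) = 0.0360/0.9480 = 3.80%; OR 1.221.

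ORs when q and m do not differ by predictor (true 1.263):

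| Deaths untested | m = 0 | m = 5% | m = 10% | m = 30% |
|---|---|---|---|---|
| 5% | 1.254 | 1.263 | 1.274 | 1.325 |
| 10% | 1.244 | 1.253 | 1.263 | 1.314 |
| 25% | 1.213 | 1.221 | 1.230 | 1.276 |
| 50% | 1.155 | 1.161 | 1.168 | 1.205 |

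If deaths are untested 30% exposed against 20% unexposed, with m = 5%, the OR is 1.177; with 20% against 30% it is 1.267.

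**3. Lower mortality.** With d = 0.4% and 0.2%, the other inputs unchanged and m = 5%, the true OR is 1.065 (3.4% against 3.2%). The rule gives 1.062 (q = 10%) or 1.052 (q = 25%).

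**4. MAKE7, adjusted.** Assumed: a measured binary covariate, present in half, with e = 4% or 2%, d multiplied by 4/3 or 2/3, and exposure 60% or 40% by covariate level. A logistic model with exposure and covariate, fitted to expected cell counts, gives 1.265 on full data. With survivors tested 95%/95%, 95%/70% or 90%/50% by covariate level, and q = 10% or 25%, the current rule gives 1.222 to 1.299.

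**5. 30-day death, if the exclusion applies.** Write dE for early death (within 7 days) and dL for later death. Odds under the rule = [dE(1−q) + dL(1−m)] / [(1−dE−dL)(1−m)]. With q and m equal across groups, the OR is unbiased if dE and dL have the same exposed-to-unexposed ratio, or if q = m. With q = 25%:

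| Early death | Later death | True OR | m = 0 | m = 5% | m = 30% |
|---|---|---|---|---|---|
| 2% vs 1% | 1% vs 0.5% | 2.031 | 2.031 | 2.031 | 2.031 |
| 2% vs 1% | 1% vs 1% | 1.515 | 1.443 | 1.456 | 1.533 |
| 1% vs 1% | 2% vs 1% | 1.515 | 1.588 | 1.575 | 1.498 |

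In the first two rows the exposed group's true 3.0% risk reads as 2.51% (m = 0) to 3.14% (m = 30%). Without the exclusion, the true value is recovered in every row.

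**6. Alternatives for MAKE7.** Suppose survivors with a creatinine rise are tested 90% of the time and others 70%. Counting all deaths and weighting tested survivors gives 1.220 against a true 1.263. The current rule gives 1.263, 1.230 and 1.168 with 10%, 25% and 50% of deaths untested. Keeping all deaths but simply dropping untested survivors gives 1.337 at 30% random missingness.

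**The case against.** Several objections have force.

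- **The 30-day point is an inference.** The sentence contrasts exposures, so it may mean only that the criteria stay the same from one predictor to the next. The analysis paragraph models only the primary endpoints, and 30-day death is not listed as one. A reader might infer that the plan definitely applies the exclusion to 30-day death. The text does not go that far. It does place one list directly after that outcome and defines no other mortality cohort, so clarification is needed either way.
- **No consequence is documented.** A reader might infer material bias, or bias towards the null. Neither follows. The table moves in both directions, Aim 3 concerns association rather than absolute risk, and at low mortality almost nothing changes.
- **The RRT component hardly matters.** Starting RRT without any creatinine in 7 days should be rare, and no scenario above depends on it.
- **Requiring an outcome measurement is an ordinary complete-case choice,** and step 6 shows that the obvious alternative can be worse. This stands, and is why the planned MAKE7 analysis should remain primary.
- **Testing may be nearly complete.** The figure below 5% is for CKD patients at 48 hours; at 7 days it can only be equal or lower in those patients. But Aim 3 is not confined to CKD, and the figure is not split by vital status, so it does not show how often early deaths go untested. Nor does the discharge provision in section F show that testing is often missed: it concerns trial patients, not the 2008–2018 cohort.

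**Conclusion.** The concern holds as a narrow gap in definition. By the wording of C.23, an untested death within 7 days meets MAKE7 and is excluded, and nothing in the Aim 3 analysis paragraph or the SAP repairs this. That the exclusion also reaches 30-day death is the most natural reading, not a certain one.

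Size and direction are unknown. On the assumed rates (7-day death 2% against 1%, creatinine events 3%), with testing that does not differ by predictor, a true MAKE7 OR of 1.263 reads as 1.21 to 1.31 with 10% or 25% of deaths and 0% to 30% of survivors untested. Extending the range to 5% to 50% of deaths untested gives 1.155 to 1.325. For 30-day death, the OR is unbiased under the two conditions in step 5; otherwise a true 1.515 reads as 1.44 to 1.59 with 25% of early deaths untested.

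Severity is minor. A reader might carry the point over to the randomised comparison, but the exclusion belongs to Aim 3 alone, so Aims 1 and 2 are unaffected.

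**What to change.** 1. State that the post-procedure creatinine exclusion does not apply to the 30-day death analysis. This is one line in the cohort definition, uses data already held, and settles the ambiguity.
2. Keep the exclusion for the creatinine-based AKI outcome.
3. Keep the planned MAKE7 analysis as primary. Add a sensitivity analysis that counts every 7-day death or RRT start whatever the creatinine status, and handles untested survivors by inverse-probability weighting or multiple imputation. State that it assumes survivors' creatinine outcomes are missing at random and that it is not uniformly closer to the truth. Do not keep the deaths while simply dropping untested survivors.
4. Report the number of patients without a post-procedure creatinine by 7-day vital status and predictor level. This table would show whether the issue matters.

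The cost is one sentence, one extra analysis and one table, with no new data collection. The drawback is that cohorts will differ between outcomes, which the report must make clear.

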Impact: Evidence of the efficacy of Virtual Learning Collaborative, augmented by Automated Surveillance Reporting, on the sustained use of preventive interventions will enable hospitals to improve quality of care for the over 2 million patients undergoing cardiac catheterization and, as a result, reduce their significant risk of acute kidney injury. More broadly, these findings will be relevant to supporting hospital's implementation of a wide array of preventive interventions and has the potential for vastly improving patient care and outcomes.

Specific Aim 3: Laboratory Predictors of AKI in Patients Undergoing Coronary Angiography

In this aim, our goal is to examine whether lower serum magnesium, lower hemoglobin, higher hemoglobin A1c, and other laboratory predictors are associated with a higher risk of AKI in patients undergoing coronary angiography. We are defining AKI as a doubling of serum creatinine (SCr) or need for RRT. We will also examine whether laboratory predictors are associated with an increased risk of death at 30 days.

A. Background and Significance:

Over two million diagnostic or interventional cardiac catheterization procedures are performed in the United States each year.^{6,15} Acute kidney injury (AKI) is preventable but occurs in up to 14% of all patients following a procedure and up to 50% in patients with pre-existing chronic kidney disease (CKD),¹ making AKI one of the most prevalent adverse events.^{2,3,7} Reducing the prevalence AKI is a patient safety objective set forth by the National Quality Forum.¹⁶ When AKI occurs, patients have an increased risk of

[figure not shown]
PROTOCOL

(Version #: 6, version date: 9-21-20)

cardiovascular events, prolonged hospitalization, end-stage renal disease, all-cause mortality, and increased acute care costs of over \$7,500 per case.^{8,11,17} Based on our preliminary evidence in our pilot demonstrating a statistically significant 28% reduction in AKI in patients with pre-existing CKD, we estimate that over 70,000 AKI events could be prevented with an annual cost savings of \$525 million each year nationally using evidence based strategies delivered through a Virtual Learning Collaborative (VLC) in common diagnostic procedures using contrast dye.

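### Aim 3 asks about predictors of AKI, but both of its primary endpoints add death, and no stated analysis separates a predictor of early death from a predictor of AKI

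*Protocol*

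**What the plan says.** The Specific Aims and section C.23 of the Protocol put the same question: whether lower magnesium, lower hemoglobin, higher hemoglobin A1c and "other laboratory predictors are associated with a higher risk of AKI in patients undergoing coronary angiography". Both places then fix the meaning of AKI: "We are defining AKI as a doubling of serum creatinine (SCr) or need for RRT". Death is not part of that definition.

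The endpoint paragraph of C.23 reads "Primary Endpoints: Major Adverse Kidney Event within 7 days (MAKE7_1 or MAKE7_2), defined as" a creatinine rise of at least 1.5-fold or at least 2-fold within 7 days, "need for RRT within 7 days, or death within 7 days". Taken in order, MAKE7_1 uses the 1.5-fold threshold and MAKE7_2 the 2-fold threshold. Death belongs to both.

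The statistical paragraph of C.23 is short: "We will conduct a multivariate analysis for the outcome of the primary endpoints as noted above", with adjustment for demographics, laboratory tests, medications and clinical conditions. It names no model by component and does not say how death before AKI is handled. Mortality is also a separate question: "We will also examine whether laboratory predictors are associated with an increased risk of death at 30 days". Among the exclusions is "No post-procedure SCr available within 7 days". The SAP describes only the randomized comparison and does not mention Aim 3.

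**The concern.** The question, the definition and the modelled outcome do not match. The question and the definition concern kidney injury. The outcome named for the model concerns kidney injury or death, and in MAKE7_1 the kidney part is milder than the definition.

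An association with a composite is a weighted mixture of the associations with its parts. If a marker is related to death within 7 days but not to creatinine or RRT, the composite can still show an association. A positive MAKE7 result therefore does not by itself answer whether the marker is associated with AKI. What is at stake is whether the conclusion of Aim 3 follows from the analysis written down for it.

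**Working it through.** **1. Text comparison (all from the Protocol).**

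| Element | Creatinine | RRT | Death | Window |
|---|---|---|---|---|
| AKI as Aim 3 defines it | doubling | yes | no | not stated in the definition |
| MAKE7_1 | ≥1.5-fold | yes | yes | 7 days |
| MAKE7_2 | ≥2-fold | yes | yes | 7 days |
| Separate mortality outcome | no | no | yes | 30 days |

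Neither composite equals AKI as defined. MAKE7_2 without death would equal it, with a 7-day window. The 30-day death outcome does not recover the difference: its window is longer, and it does not split MAKE7 into parts. A marker positive on both MAKE7 and 30-day death could act through kidney injury, through death, or through both.

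**2. Figures in the plan.** For Aim 3 the documents give no event rate, sample size, alpha or power, so there is nothing to reproduce. Everything below is illustration on assumed inputs.

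**3. Composite risk ratio.** Let K be the risk of a kidney event and D the risk of death without one. The marker has risk ratio 1 for K and 2 for D.

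- Death share of composite events = D / (K + D)
- Composite risk ratio = (K + 2D) / (K + D)

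| K | D | Death share | Composite risk ratio |
|---|---|---|---|
| 1% | 1% | 1/2 = 50% | 3/2 = 1.50 |
| 1.5% | 0.8% | 0.8/2.3 = 35% | 3.1/2.3 = 1.35 |
| 2% | 0.5% | 0.5/2.5 = 20% | 3/2.5 = 1.20 |
| 5% | 0.5% | 0.5/5.5 = 9% | 6/5.5 = 1.09 |
| 10% | 0.5% | 0.5/10.5 = 5% | 11/10.5 = 1.05 |

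The upper rows suit a doubling threshold if such events are rare. The lower rows suit the 1.5-fold threshold of MAKE7_1, where kidney events are commoner and death weighs less.

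**4. Chance of a significant composite result.** Further assumptions: the marker is present in 10% of patients, the test is two-sided at 0.05, there is no covariate adjustment, and death is independent of AKI. D is now all death within 7 days. The composite risk is 1 − (1 − K)(1 − D) without the marker and 1 − (1 − K)(1 − 2D) with it. For example, K = 5% and D = 1% give 1 − 0.95 × 0.99 = 0.0595 and 1 − 0.95 × 0.98 = 0.0690. The power is that of a comparison of two proportions.

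| K | D | Odds ratio | N = 20,000 | N = 100,000 |
|---|---|---|---|---|
| 10% | 0.5% | 1.05 | 9% | 29% |
| 5% | 1% | 1.17 | 40% | 96% |
| 2% | 1% | 1.34 | 66% | nearly 100% |
| 2% | 2% | 1.53 | 97% | nearly 100% |

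Over all the combinations tried (K of 2%, 5% and 10%; D from 0.2% to 2%), the chance ran from about 5% to 97% at N = 20,000 and from about 8% to nearly 100% at N = 100,000.

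Both values of N are assumptions. Section A.4 mentions 115,633 VA patients in earlier work, and C.16.c more than 510,000 patients and procedures for 2000 to 2024. Neither is the Aim 3 cohort, which covers 2008 to 2018 and requires baseline creatinine, post-procedure creatinine and the marker itself.

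**The case against.** A reader might infer that a marker predicting only death would be reported as a predictor of AKI. The documents do not support that. They set no such reporting rule, call the composite a major adverse kidney event, keep AKI as a separate definition, and examine 30-day death in its own right. In describing earlier cardiac surgery work, C.23 itself distinguishes a composite that includes death from AKI alone.

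Other points in the plan's favor:

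- The AKI definition stands inside the endpoint paragraph, so the analysis sentence could be read as covering AKI too. That reading is possible, but the text does not state it, and the ambiguity needs settling.
- The exclusion of patients without creatinine within 7 days removes some early deaths, and covariate adjustment may absorb part of a pathway through general illness. Both would shrink the effect. Neither removes deaths that follow a creatinine measurement, and neither splits the composite.
- Counting death in a 7-day composite and again in a 30-day outcome is overlap, not an error.
- Including death in a kidney composite is a defensible way to deal with patients who die before creatinine can rise. Whether the composite should stay primary is partly a matter of preference.
- The plural heading suggests that both composites will be analyzed. It does not say which would carry the conclusion.

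What stands is that no clearly stated analysis estimates the association with AKI as the aim defines it.

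**Conclusion.** The mismatch is real and can be read directly from the Protocol. A marker related to early death but not to kidney injury could be positive on a primary endpoint, and the stated analyses would not separate it from a predictor of AKI. The documents do not go further than that: whether any of the named markers behaves this way, and whether the result would be significant, cannot be determined from them.

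The illustrated composite risk ratio of about 1.05 to 1.50 rests on assumed event rates and an assumed risk ratio of 2 for death. It shows only that the effect may be negligible or material depending on death's share of events. The matter is confined to an observational aim. It leaves Aims 1 and 2 untouched and is worth correcting mainly because correction is cheap.

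**What to change.** In the statistical paragraph of C.23:

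1. Add a model for AKI as the aim defines it (doubling of creatinine or RRT) with a stated 7-day window, treating death before AKI as a competing event and naming the method.
2. State that any conclusion about AKI rests on that model.
3. Report the creatinine, RRT and death components of MAKE7_1 and MAKE7_2 separately.

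Alternatively, restate the Aim 3 question in terms of MAKE7, name which version is primary, and still report the components.

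The cost is Protocol wording and a little more analysis. No new data are needed, because the components must be known to build the composites. The AKI-only model will have fewer events than either composite, so its estimates will be somewhat less precise.
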